5.6 Day 7 Follow-up (+/- 1 day)

Subjects will return to the clinic on day 7, and the following procedures will be performed:

- 1) Physical examination. Brief physical examination (body weight and vital signs with nursing physical assessment) including symptom directed physician physical examination as required by patient symptoms. Vital signs will include blood pressure, pulse, respiratory rate and oral temperature (use standard electronic oral thermometer provided by Sponsor);
- 2) Collection of two nasopharyngeal swabs using nylon flocked dry swabs (Copan Diagnostics) for RT-PCR and culture;
- 3) Collection of blood sample for laboratory safety tests including hemoglobin, hematocrit, complete blood count (total and differential), platelet count, random blood sugar, total cholesterol, HDL, LDL, triglycerides, albumin, AST, ALT, GGT, alkaline phosphatase, bilirubin (total/direct), BUN, creatinine, sodium, potassium, chloride;
- 4) Collection of urine sample for routine urinalysis (glucose, protein and blood);
- 5) Review of compliance with study medication, collection of medication bottle with any unused medications, and completion of the pill count log form;
- 6) Review and recording of concomitant medications; and
- 7) Review and recording of adverse events/side effects.

5.7 Day 22 Follow-up (+ 3 days)

Subjects will return to the clinic on day 22, and the following procedures will be performed:

- 1) Physical examination. Brief physical examination (body weight and vital signs with nursing physical assessment) including symptom directed physician physical examination as required by patient symptoms. Vital signs will include blood pressure, pulse, respiratory rate and oral temperature (use standard electronic oral thermometer provided by Sponsor);
- 2) Collection of two nasopharyngeal swabs using nylon flocked dry swabs (Copan Diagnostics) for RT-PCR and culture (to be tested for presence of virus only if the sample collected at the preceding time point had detectable virus);
- 3) Collection of blood sample for anti-influenza antibodies;
- 4) Review and recording of concomitant medications; and
- 5) Review and recording of adverse events/side effects. Note that all adverse events must be followed until their resolution or stabilization even beyond the 22-day study period.

5.8 Unscheduled Visit

Subjects returning to the clinic for an unscheduled visit due to worsening symptoms or adverse events will be evaluated at the discretion of the Investigator as is medically warranted. Tests and/ or procedures performed at this visit may include, but are not limited to the following.

- 1) Physical examination. Brief physical examination (body weight and vital signs with nursing physical assessment) including symptom directed physician physical examination as required by patient symptoms. Vital signs will include blood pressure, pulse, respiratory rate and oral temperature (use standard electronic oral thermometer provided by Sponsor);

- 2) Collection of two nasopharyngeal swabs using nylon flocked dry swabs (Copan Diagnostics) for RT-PCR and culture;
- 3) Collection of blood sample for laboratory safety tests including hemoglobin, hematocrit, complete blood count (total and differential), platelet count, random blood sugar, total cholesterol, HDL, LDL, triglycerides, albumin, AST, ALT, GGT, alkaline phosphatase, bilirubin (total/direct), BUN, creatinine, sodium, potassium, chloride;
- 4) Collection of urine sample for routine urinalysis (glucose, protein and blood);
- 5) Review of compliance with study medication;
- 6) Review and recording of concomitant medications; and
- 7) Review and recording of adverse events/side effects.

5.9 Study Discontinuation

Rules for discontinuation of a patient or for discontinuing the study are provided in section 11.2. All subjects discontinued from the study before day 7 will be evaluated at study discontinuation using the procedures described above for day 7. All subjects discontinued from the study after day 7 will be evaluated at study discontinuation using the procedures described above for day 22.

5.10 Electronic Subject Diary

Electronic subject diaries will be completed twice daily through day 21. The electronic diaries will capture the following information:

- 1) Medication intake (twice daily at time of medication intake).
- 2) Oral temperature (twice daily at time of medication intake). Use standard electronic oral thermometer provided by Sponsor. Oral temperature should, preferably, be recorded prior to acetaminophen dosing or greater than 4 hours after acetaminophen dose.
- 3) Use of other medications taken (including acetaminophen) by the subject not previously captured in the subject's medication history. Document in detail including dose in milligrams or other applicable units, time of ingestion, and the reason for use of the medication (at time of medication intake).
- 4) FLU-PRO Questionnaire (once daily between 7 pm and 11 pm) to characterize symptoms of influenza.
- 5) Activity assessment using an 11-point visual analog scale (0= unable to perform normal activity, 10= fully able to perform normal activity) (once daily between 7 pm and 11 pm).
- 6) Adverse experiences (once daily between 7 pm and 11 pm).

5.11 Plan for Virology Testing and Monitoring Resistance

In an effort to monitor potential resistance to tizoxanide during study RM08-3004, the following procedures will be performed:

- 1) Collection of samples:
Two nasopharyngeal swabs will be collected from each patient at Baseline (day 1) and days 2, 3, 7 and

- 22.
- 2) Testing of biological samples
 - a. Each Baseline sample will be subjected to: (1) culture to detect influenza A and B, (2) RT-PCR using the ePlex[®] Respiratory Pathogen Panel (GenMark, Carlsbad, CA) to detect influenza A (non-specific as to subtype); influenza A H1, H1N1 (2009), H3 subtypes; influenza B; respiratory syncytial virus A and B (RSV); parainfluenza 1, 2, 3 and 4; human metapneumovirus (hMPV); adenovirus (A-F); human rhinovirus/enterovirus; coronavirus NL63, HKU1, 229E and OC43; *Chlamydomphila pneumoniae*; and *Mycoplasma pneumoniae*.
 - b. If a subject's Baseline sample is negative for influenza by RT-PCR, his/her day 2 and day 3 samples will be subjected to RT-PCR using the ePlex[®] Respiratory Pathogen Panel to detect respiratory pathogens.
 - c. If the Baseline sample or the day 2 or day 3 sample is positive for influenza A or influenza B, the Baseline sample and each of the day 2 and 3 samples will be subjected to TCID₅₀ to quantify viral shedding.
 - d. Day 7 samples will be subjected to culture and RT-PCR using the ePlex[®] Respiratory Pathogen Panel. All samples positive for influenza A or influenza B will also be subjected to TCID₅₀ to quantify viral shedding.
 - e. Day 22 samples will be subjected to culture and RT-PCR using the ePlex[®] Respiratory Pathogen Panel only if the sample collected at the preceding time point (day 7) had detectable influenza virus. All samples positive for influenza A or influenza B will also be subjected to TCID₅₀ to measure viral shedding.
 - 3) Drug susceptibility testing
 - a. If any day 7 or day 22 sample is positive for influenza A or influenza B by culture, the virus will be isolated and tested for susceptibility to tizoxanide (TCID₅₀).
 - b. The Baseline isolate for subjects with virus cultured at day 7 or 22 will also be tested for susceptibility to tizoxanide, and the results will be compared to the results observed for the day 7 or 22 isolate.
 - 4) Nucleotide sequencing
 - a. All day 7 or 22 samples with reduced susceptibility (IC₅₀ >2x IC₅₀ at Baseline) or resistance (IC₅₀ ≥10x IC₅₀ at Baseline) to tizoxanide will be subjected to hemagglutinin and neuraminidase nucleotide sequencing. The corresponding Baseline sample will also be subjected to hemagglutinin and neuraminidase nucleotide sequencing. Initial genotypic assessments of resistance to tizoxanide will focus on isolates displaying the largest shifts in susceptibility.
 - b. Sequencing data for day 7 or 22 isolates with reduced susceptibility or resistance to tizoxanide will be compared to sequence data for the Baseline sample to identify mutations that may confer resistance.
 - 5) Storage of samples: All samples collected during the study will be stored for at least 2 years for potential future testing.
 - 6) Clinical Virology Laboratory:

5.12 Pregnancy

Fertility and reproduction studies in animals have revealed no evidence of impaired fertility or harm to the fetus due to NTZ. There are, however, no adequate and well controlled studies of fertility or reproduction in humans. All pregnancies including those of partners of male subjects included in the study will be reported by the investigational staff within 24 hours of their knowledge of the event using a pregnancy reporting form.

6 RANDOMIZATION

An independent third party ([REDACTED]) will prepare a master randomization list and maintain the masking of the study. Randomization will be performed using permuted block randomization. Blocks of masked study medication will be assigned to each Investigator. Each Investigator will then assign treatment numbers to subjects who qualify for the study using centralized randomization procedures stratified by time since symptom onset for each subject (<24 hours, >24-36 hours, and >36 hours). The treatment numbers will appear on the bottles containing the masked study medication. The randomization list will be masked to study participants including Sponsor, Investigators, study monitors, subjects and laboratory personnel. Unmasking for any individual patient will occur only if necessitated by emergency and knowledge of the medication being taken will influence the medical management of the subject. Furthermore, if the event warrants submission of an IND Safety Report, then the subject will be unmasked for completion of the report.

7 DATA MANAGEMENT

7.1 Electronic Data Entry

[REDACTED]

is a source data collection solution that will allow the site staff to record subject data on their source forms by using tablets provided by [REDACTED]. Its purpose is to eliminate the need for data transcription into a traditional electronic case to allow both real-time access to source data by authorized Sponsor personnel and real-time edit checks.

is a mobile application for the capture of patient-reported outcomes (PROs). Study staff will use [REDACTED] on their own smartphones or a provisioned device provided by [REDACTED], in order to record PROs, concomitant medications and adverse events (in the form of an electronic subject diary) and to receive personalized study-specific reminders and education.

is the [REDACTED] web portal. It delivers real-time access to source data, and enables study personnel to review, clean and analyze study data.

The site staff will use [REDACTED] as they meet with study subjects and perform study procedures. Computerized data checks will be used in addition to manual review including listings review, to check for discrepancies and to ensure consistency and completeness of the data.

The responsible study monitor(s) will verify data, which can be performed remotely or at the clinical study site. The Investigator will ensure that the data recorded are accurate and complete.

Queries emerging during data cleaning will be generated by data management or clinical research associates in [REDACTED]. The Investigator or his/her designee will answer the queries and update the source data.

Adverse events will be coded by data management using the latest version of the Medical Dictionary for Regulatory Activities (MedDRA); medications will be coded by data management using the latest version of the World Health Organization (WHO) Drug Dictionary.

After the Last Subject Last Visit (LSLV) has taken place, the database will be cleaned as necessary. As soon as the database is considered clean, it will be locked. The locked database will be used in the final statistical

analysis for study reporting. Measures will be undertaken to protect subject data handled during inspections against disclosure to unauthorized third parties. Subject confidentiality will be maintained at all times.

All listings, summaries and analyses will be produced using SAS Statistical Software (SAS Institute, Inc., Cary, NC).

7.2 Protocol Deviations

Protocol deviations will be documented by the Investigator, reported to the institutional review board (IRB) as appropriate, and also reviewed by the assigned clinical research associate (CRA). Deviations will be reported in the electronic data capture system. Each deviation will be classified as major or minor according to the following definitions:

Major protocol deviation: A deviation that has an impact on subject safety, may substantially alter risks to subjects, may have an effect on the integrity of the study data, or may affect the subject's willingness to participate in the study

Minor protocol deviation: All other protocol deviations.

7.3 Data Quality Assurance

The accuracy and reliability of the study data will be assured by the selection of qualified Investigators and appropriate study centers, review of protocol procedures with the Investigator and associated personnel prior to the study, and by periodic monitoring visits by the Sponsor. Written instructions will be provided for collection, preparation, and shipment of samples.

The monitor will review the source data for accuracy and completeness, and any discrepancies will be resolved with the Investigator or designee, as appropriate.

[figure not shown]
The Sponsor will be entitled to inspect and audit the facilities used in the clinical and laboratory parts of the study, as well as to make anonymized copies of all the data files pertaining to the study. Similar procedures may also be conducted by agents of any regulatory body, either as part of a national GCP compliance program or to review the results of this study in support of a regulatory submission. The Investigator should immediately notify the Sponsor if they have been contacted by a regulatory agency concerning an upcoming inspection.

8 STATISTICAL CONSIDERATIONS

8.1 Sample Size Calculation

As described in section 7.3 below, the Symptom Response definition for this study will be derived from the subjects' FLU-PRO questionnaire responses. The FLU-PRO-derived endpoint is expected to track very closely to return to usual health status (a daily yes/no question in the FLU-PRO questionnaire). Patient-reported outcomes for time to return to usual health status have been shown to track very closely with time to ability to perform 100% of usual activities.^{27,28,29} We assume, therefore, that the cumulative distributions of time to Symptom Response for the placebo treatment group will closely reflect historical data (Romark studies RM08-3002 and RM08-3003 and oseltamivir studies WV15670 and WV15671) for time from first dose until the subjects report that they are able to perform 100% of usual activities. Based upon data from Romark studies RM08-3001, RM08-3002 and RM08-3003, we assume that treatment with NTZ should result in reduction of at least 40 hours in median time to symptom response with differences being less at the first

quartile and greater at the third quartile. Based upon this historical data, the following curves have been developed for determining sample size.

Based upon these curves, a sample size of 552 subjects with laboratory-confirmed influenza (i.e. 276 for each of the 2 groups) will provide 90% power to detect a statistically significant difference in the survival distributions between NTZ and placebo groups (2-sided alpha of 0.05). This calculation was performed for the Gehan rank test using SAS PROC POWER (SAS 9.4) with the curves shown above (proportion not recovering by the end of each day was used as input) and censoring at day 21 (hour 504). Assuming that 8% of subjects will have incomplete data, we arrive at a sample size of 600 subjects in total, 300 per treatment group to yield at least approximately 550 with complete data (all 600 subjects will be included in the primary analysis with subjects with incomplete data censored as of their last entry).

Based upon these calculations, the study will enroll at least 600 subjects with laboratory-confirmed influenza up to a maximum of 700 subjects with laboratory-confirmed influenza. We estimate that this will require enrollment of 800 to 1,200 subjects in total assuming a flu-positive rate between 50% and 75%.

8.2 Efficacy Variables

Primary Efficacy Parameter: Time from first dose until Symptom Response

Secondary Efficacy Parameters:

- i. Time from first dose until subjects are able to perform 100% of normal activities (i.e., a score of 10 on the scale of 0-10)
- ii. Proportions of subjects experiencing one or more complications of influenza including pneumonia, otitis media, bronchitis, sinusitis, worsening of pre-existing health conditions, systemic antibiotic use for infections secondary to influenza infection, hospitalization due to influenza or complications of influenza and death
- iii. Time to Symptom Response excluding the FLU-PRO Gastrointestinal and Eye domains

Exploratory Efficacy Parameters:

- i. Time to Individual Symptom Response
- ii. Time to FLU-PRO Domain Response
- iii. Time to Resolution of Acute Febrile Illness
- iv. Time to Return to Usual Health

- v. Change in influenza virus titer (TCID₅₀) from baseline to day 2 and from baseline to day 3
- vi. Proportions of subjects with virus detected in nasopharyngeal swabs collected at each of days 2, 3 and 7 by culture and by RT-PCR

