- The primary efficacy analysis will be repeated using only items from the four FLU-PRO domains (Body/Systemic, Throat, Chest/Respiratory and Nose) that correspond to the seven symptoms included in the traditional PRO instrument (feverishness, myalgia, headache, fatigue, sore throat, nasal obstruction and cough). For this secondary analysis, we will derive the Symptom Response definition in the same manner as for deriving the Symptom Response definition used in the primary analysis (after removing the Eye and Gastrointestinal symptoms).

Exploratory analyses will be performed as follows:

- For each of the 32 individual FLU-PRO symptoms, Time to Individual Symptom Response for the NTZ and placebo treatment groups will be compared using the Gehan-Wilcoxon test.
- For each of the 6 FLU-PRO domains, Time to FLU-PRO Domain Response for the NTZ and placebo treatment groups will be compared using the Gehan-Wilcoxon test.
- Time to Resolution of Acute Febrile Illness for the NTZ and placebo treatment groups will be compared using the Gehan-Wilcoxon test.
- Time to Return to Usual Health for the NTZ and placebo treatment groups will be compared using the Gehan-Wilcoxon test.
- Changes in influenza TCID₅₀ viral titers from baseline to day 2 and from baseline to day 3 for the NTZ and placebo treatment groups will be compared using a t-test.
- For subjects with laboratory-confirmed influenza, the proportions of subjects with influenza virus detected by culture in nasopharyngeal swabs collected at each of days 2, 3 and 7 will be compared for the two treatment groups using a Fisher's exact test.

Sensitivity analyses for the primary endpoint will include:

- Repeat the primary efficacy analysis, assigning a Time to Symptom Response of 21 days for subjects that discontinue prior to day 21 without achieving Symptom Response.
- Repeat the primary efficacy analysis for a “per protocol” subset.

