7. STUDY DESCRIPTION

7.1 Study Objectives

The primary objective of this study is to evaluate the effect of nitazoxanide (NTZ) administered orally 600 mg b.i.d. with food for 5 days in reducing the duration of symptoms of influenza compared to that of a placebo.

A key secondary efficacy objective is to evaluate the effect of NTZ compared to placebo on time to return to ability to perform all normal activities.

Other secondary efficacy objectives include evaluating the effect of NTZ compared to placebo on:

- a) the proportion of subjects experiencing one or more complications of influenza including pneumonia, otitis media, bronchitis, sinusitis, worsening of pre-existing health conditions, systemic antibiotic use for infections secondary to influenza infection, hospitalization due to complications of influenza, and death; and
- b) the duration of symptoms of influenza during 21 days of follow up based upon the four FLU-PRO domains (Body/Systemic, Throat, Chest/Respiratory and Nose) that correspond to the seven symptoms included in the traditional patient-reported outcomes instrument (feverishness, myalgia, headache, fatigue, sore throat, nasal obstruction and cough).

Exploratory efficacy objectives include evaluating the effect of treatment with NTZ on the time to response for each FLU-PRO symptom, time to response for each FLU-PRO domain, time to resolution of febrile illness, time to return to usual health, and changes in viral titers from baseline to each of days 2, 3 and 7.

Other important objectives include evaluation of the safety of NTZ by analysis of adverse events and evaluation of the effect of nitazoxanide on influenza antibody response and evaluation of relationships between pharmacokinetics and clinical or virologic responses.

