Analysis Population(s):	Confirmed Influenza
Derived Variables:	Event: Time of Ability to Perform All Normal Activities – time of the first dose Censored: Time of last ability assessment – time of the first dose

10.5.5 Change in Influenza Virus Titer (TCID₅₀) from Baseline to Day 2 and from Baseline to Day 3

Variables Used for the Analysis

The analysis will require the following variables:

Variable	Source	Format/Notes
TCID ₅₀ virus titer	Laboratory data	TCID ₅₀ values will be reported as “10 ^{-3.2} ”, for example. For analysis purposes, the values should be negative log-transformed. For the example above, the analysis value would be “3.2”.

Analysis

Mean changes in influenza viral titers from baseline to day 2 and from baseline to day 3 for the NTZ and the placebo treatment groups will be compared using a t-test.

Analysis Population(s):	Confirmed Influenza
Derived Variables:	Mean change in influenza viral titer from baseline to day 2: mean of (day 2 TCID ₅₀ value – baseline TCID ₅₀ value) for each subject within the treatment groups Mean change in influenza viral titer from baseline to day 3: mean of (day 3 TCID ₅₀ value – baseline TCID ₅₀ value) for each subject within the treatment groups

10.5.6 Proportions of Subjects with Detectable Virus at Days 2, 3 and 7

Variables Used for the Analysis

The analysis will require the following variables:

Variable	Source	Format/Notes
TCID ₅₀ virus titer	Laboratory data	TCID ₅₀ values will be reported as “10 ^{-3.2} ”, for example. For analysis purposes, any numerical result will be treated as “positive”. A result of “No Virus Isolated” will be treated as “negative”.

Analysis

The proportion of subjects with a positive result by TCID₅₀ at each of days 2, 3, and 7 will be compared across treatment groups using a Fisher’s exact test.

Analysis Population(s):	Confirmed Influenza

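### The virus-detection endpoint is defined in three ways, Day 7 RT-PCR and culture are never compared between arms, and SAP 10.5.6 counts subjects with no Day 7 TCID50 result as virus-negative

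*Protocol*

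**What the plan says.** **Detection endpoint.** Protocol 8.2, exploratory item vi, names two assays at three visits: "Proportions of subjects with virus detected in nasopharyngeal swabs collected at each of days 2, 3 and 7 by culture and by RT-PCR". Protocol 8.4.1, which gives the test, keeps one assay: "the proportions of subjects with influenza virus detected by culture in nasopharyngeal swabs collected at each of days 2, 3 and 7", by Fisher's exact test. SAP 10.5.6 uses a different measure, starting "The proportion of subjects with a positive result by TCID" (the assay is TCID50), at Days 2, 3 and 7, also by Fisher's exact test.

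**What is tested.** Protocol 5.11, item 2(d), sets no condition for the last of these visits: "Day 7 samples will be subjected to culture and RT-PCR using the ePlex" panel. It continues: "All samples positive for influenza A or influenza B will also be subjected to TCID₅₀ to quantify viral shedding". At Days 2 and 3, item 2(b) runs RT-PCR only when the baseline RT-PCR was negative for influenza, whereas Protocol 5.5 describes the Day 2 and 3 swabs as if all of them had RT-PCR.

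**Day 7 rule.** For Days 2 and 3, SAP 10.5.6 divides by subjects who have a TCID50 result. For Day 7 it divides by all confirmed-influenza subjects and takes a missing result as negative, because samples negative on traditional culture were not titrated.

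**Titer change.** The exploratory objective in Protocol 2 and SAP 7.1 covers "changes in viral titers from baseline to each of days 2, 3 and 7". Protocol 8.2, item v, covers only change "from baseline to day 2 and from baseline to day 3". Protocol 8.4.1 and SAP 10.5.5 stop at Day 3 too.

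**The concern.** One endpoint has three definitions, and the SAP's version contains neither RT-PCR nor traditional culture as such. Day 7 is the only one of the three visits at which RT-PCR is scheduled for the whole confirmed-influenza population. There the results go to the Virology Data listing (SAP 10.7) and to no table.

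The Day 7 measure that replaces them turns an absent result into evidence of clearance. If swab attendance differs between arms, a difference in attendance would appear as a difference in viral clearance. If the choice of assay is left open until after unblinding, any later RT-PCR comparison would look selected. The objective also promises a Day 7 titer result that no section produces.

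**Working it through.** No figure in the plan needs reproducing. The check sets the sections side by side.

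| Source | Detection: assay | Detection: days | Titer change: days |
|---|---|---|---|
| Protocol 2 and SAP 7.1 (objective) | not named | – | 2, 3, 7 |
| Protocol 8.2 (v, vi) | culture and RT-PCR | 2, 3, 7 | 2, 3 |
| Protocol 8.4.1 | culture | 2, 3, 7 | 2, 3 |
| SAP 10.5.5 and 10.5.6 | TCID50 | 2, 3, 7 | 2, 3 |

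**Count of between-arm comparisons.** Protocol 8.2(vi) implies 2 assays × 3 days = 6 detection comparisons. Protocol 8.4.1 has 1 × 3 = 3, all by culture. SAP 10.5.6 has 1 × 3 = 3, all by TCID50. The SAP has 0 by RT-PCR; display 14.2.11 in its Appendix II is the TCID50 analysis. For titer change, the objective names 3 visits and the analysis sections cover 2, so 1 of 3 is unanalysed.

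**What 5.11 can deliver.** RT-PCR for the whole population exists only at Day 7, so 1 of the 3 RT-PCR comparisons in 8.2(vi) can be made in full. Traditional culture is also scheduled at Day 7. At Days 2 and 3 the only culture-type assay scheduled is TCID50. Item 8.2(vi) therefore cannot be produced as written, but its Day 7 part can.

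**Who the Day 7 rule counts as negative.** Protocol 5.11(2)(d) sends influenza-positive Day 7 samples to TCID50 and does not limit this to culture-positive ones. SAP 10.5.6 says culture-negative samples were not titrated. The two statements conflict. As worded, the SAP rule classes these subjects as virus-negative:

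1. Subjects negative on Day 7 culture, which is the group the rule was written for.
2. Subjects positive on Day 7 RT-PCR, negative on culture and left untitrated.
3. Subjects with no Day 7 swab.
4. Possibly subjects confirmed only at Day 2 or 3. Protocol 3 and SAP 7.2 say follow-up swabs from baseline-negative subjects are not titrated, while 5.11(2)(c) and (d) provide for titration. SAP 8.1 includes these subjects in the Confirmed Influenza population.

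**Size of the missing-swab effect.** Let p be the positive proportion among swabbed subjects and m the fraction with no Day 7 swab. The SAP reports p × (1 − m).

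The documents give no value for m. As an assumption, take the range 0% to 8%, the upper end being the 8% incomplete-data allowance in Protocol 8.1, with 300 subjects per arm:

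- m = 0: no subject miscounted, factor 1.
- m = 8%: 300 × 0.08 = 24 subjects per arm counted as negative, factor 276/300 = 0.92.
- Equal m in both arms: both proportions shrink, and their ratio is unchanged.
- m = 8% in one arm and 0 in the other: with no treatment effect the reported ratio is 0.92, or 1/0.92 = 1.09 in the other direction.

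**The case against.** The strongest reply is that the SAP stays close to the protocol's own analysis section. TCID50 is a tissue-culture assay, as the SAP's abbreviation list says, and at Days 2 and 3 it is the only culture-type assay scheduled. At Day 7, scoring culture-negative samples as negative makes the SAP endpoint largely follow the culture result that 8.4.1 names. This stands. The loss is mainly Day 7 RT-PCR, plus a clean Day 7 culture comparison with its own denominator.

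Three stronger readings are tempting, and the documents do not support them:

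- **That the SAP created the gap.** Protocol 8.4.1 already drops RT-PCR, and Protocol 8.2(v) and 8.4.1 already stop titer change at Day 3 ("viral titers from baseline to day 2 and from baseline to day 3 for the NTZ and placebo treatment groups will be compared"). The conflict begins within the protocol, and on these two points the SAP follows the narrower text.
- **That a virology objective goes wholly unanalysed.** Titer change at Days 2 and 3 is analysed, and Day 7 TCID50 positivity is compared. Only the Day 7 part of titer change is missing. RT-PCR clearance is in no stated objective.
- **That the SAP exchanges a well-powered endpoint for a weak one.** The documents give no Day 7 positivity rate for either assay. As an illustration only, take 280 subjects per arm, a 30% relative reduction and a two-sided 0.05 level. Exact Fisher power is then 10%, 20%, 43%, 65%, 83% and 94% at placebo positivity of 5%, 10%, 20%, 30%, 40% and 50%. Turning this into a contrast between assays requires assumed rates and the same relative effect on both, although RT-PCR may detect non-viable virus. Protocol 1.2.4 also reports that in study RM08-3001 placebo titers had fallen close to those on nitazoxanide by day 5. That lends no support to a large Day 7 effect and makes a Day 2 and 3 focus reasonable.

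**Conclusion.** The concern holds as an inconsistency to reconcile, with one substantive defect. The three assay definitions, the absence of any between-arm comparison of Day 7 RT-PCR or traditional culture, and the unanalysed Day 7 titer change all follow from the text and need no assumption. So does the conflict between 5.11(2)(d) and the SAP over which Day 7 samples are titrated.

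The defect is the Day 7 missing-as-negative rule. Its size depends on how many subjects lack a Day 7 swab, which the documents do not give; at the assumed 8% it is 24 subjects per arm. The number of RT-PCR-positive, culture-negative subjects left untitrated is also unknown.

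The consequence is small. These analyses are exploratory and lie outside the hierarchy in SAP 10.4, so the primary result and the type I error control are unaffected.

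**What to change.** 1. **SAP 10.5.6.** At Day 7, compare detection by RT-PCR and by culture side by side, each among subjects with a Day 7 result for that assay. Keep TCID50 for Days 2 and 3. This removes the rule that scores missing results as negative.
2. **Protocol 8.2(vi), 8.4.1 and 5.5.** Align them with the testing in 5.11, where Day 2 and 3 RT-PCR is run only for baseline RT-PCR-negative subjects. State once which Day 7 samples are titrated.
3. **Titer objective.** One option is to add change from baseline to Day 7 in SAP 10.5.5. It needs a stated value, for example the assay's lower limit, for swabs that were collected but not titrated because culture or RT-PCR was negative; absent swabs are missing. Without such a rule the analysis would be restricted to subjects still shedding, a selection made after randomisation. The other option is to remove Day 7 from the objective in Protocol 2 and SAP 7.1.

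The cost is some text changes and one or two more exploratory tables. The RT-PCR and culture results are already scheduled and listed. Because RT-PCR may pick up non-viable virus, it belongs beside culture and should not replace it. The choice should be fixed before unblinding.
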